Source of Subjects. The greater Baton Rouge community has between 30-40,000 adults 65 years of age or older. We will identify potentially eligible study subjects via advertising. Specifically, with the assistance of the PBRC Recruiting Core, we will recruit potential subjects from advertisements placed on the bulletin boards, electronic bulletin boards, social media, and in local and regional newspapers (e.g., the Advocate, the LSU Reveille,) and magazines. We will advertise on regional radio stations as needed. We will post flyers in senior housing establishments as well as attend senior expos. All recruitment materials will be approved by the IRB prior to their use.

SCREENING AND STUDY VISITS

Screening Visits.

Potentially eligible subjects will complete a screening visit, which we will split into two parts. We will try and schedule Part I and II on the same day, but these visits may be conducted on separate days.

Screening Visit, Part I (about 3 hours) will be conducted at PBRC and will include IRB approved written informed consent, review of inclusion/exclusion criteria, medical history, physical exam, vital signs, resting electrocardiogram, height, weight, fasting blood draw (~ 10 ml, 2 teaspoons), and Physical Activity Readiness Questionnaire for Everyone (PARQ+), the Short-Physical Performance Battery (SPPB),¹⁷ and Saint Louis University Mental Examination.¹⁸ We will peak oxygen consumption (VO₂ peak) using a cardiopulmonary exercise test¹⁶ in the Exercise Testing Core. *Prior to the completion of Part I of the screening visit, eligible subjects will be provided a map and directions on how to get to the LSU Exercise Physiology Laboratory and the School of Kinesiology Exercise Training Facility. There are reserved parking spots available through the LSU School of Kinesiology that will be reserved for Part II of the screening visit as well as study visits conducted in the LSU Exercise Physiology Laboratory or the School of Kinesiology Exercise Training Facility. We will also provide the subjects the contact information (office and cell phone number) of the study personnel assigned to meet them at each study visit and training session.*

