Screening Visit, Part II (about 2 hours) will be conducted in LSU Exercise Physiology Laboratory and will include height, weight, the completion of the International Physical Activity Questionnaire-Elderly,¹⁹ Sedentary Behavior Questionnaire,²⁰ and PROMIS Physical Function Questionnaire^{21, 22}, and the Pittsburgh Fatigability Questionnaire. We will also measure height and weight. We will measure isokinetic strength and endurance of the knee extensors (Biodek System 3) and the 1-repetition maximums (1-RMs)

for the knee extension, leg press, and chest press. Note: the 1-RM measurements may be performed prior to your regularly scheduled exercise session during the first and last week of the intervention. We will also measure grip strength using a hand dynamometer.

Baseline Physical Activity Monitoring. At the end of part II of the screening visit, all subjects who are deemed eligible to continue onto the pre-training visits described below will be provided two devices to measure their physical activity leading up to their pre-intervention testing. A wrist-worn physical activity monitor (Actigraph, GT9X) will be issued to the subjects to wear 24-h/d for 7-days (± 3 days) prior to their pre-training visits to quantify objectively their PA and ST. Subjects will also be asked to wear a second physical activity monitor (Actigraph, GT9X) on their thigh 24-h/d for 7-days (± 3 days). Subjects will be asked to return their physical activity monitors during the Pre-training Visit 1 (V1). In the event that a subject is deemed ineligible after part II of the screening visit, we would request that the subject return his/her physical activity monitors at their earliest convenience. We will screen raw data from these monitors for periods of valid wear-time with a required minimum wear-time of 10 h per valid wear-day and 4 valid wear-days per week.^{23, 24} We will use standard algorithms to characterize the patterns of PA and ST.²⁵

Baseline Dietary Record. Subjects will be asked to record their dietary intake for the 24 hrs prior to their pretraining visit 1. They also will be asked to replicate their dietary intake before posttraining visit 4. Moreover, they will be asked to refrain from consuming caffeine or participating in vigorous exercise 48 hours prior to these visits.

Pre-training Visits 1 (V1). (About 5 hours). V1 will be scheduled at least 7 days after screening visit Part II.

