The LPA breaks in ST will consist of walking at ~2 METS for 6x10 min bouts, which will be completed throughout the day, with ~1 bout per hour. Alternative 2 MET mobility-based activities may also be provided using the Compendium of Physical Activities to promote adherence. We may use text/email messaging to send reminders, the "Stand Up! The Work Break Timer" (Apple/Android App) to promote adherence to the LPA breaks in ST protocol. We may also use the CentrePoint Cloud-Based Data Capture and Management Platform to send reminders to study participants. We will initially send these reminders on the days in which the subjects do not report for their RE sessions, the frequency of these reminders may be increased or decreased based on adherence. To reduce the risk of injury and muscle soreness, we will progressively increase the intensity and volume of the exercise prescriptions to the targeted training intensities over the first month of the intervention. Prior to each training session, we will assess resting blood pressures and heart rates. We will not allow subjects to exercise if they have a resting diastolic blood pressure > 100 mm Hg, resting systolic blood pressure > 180 mm Hg, or resting heart rate > 100 beats per min. We will also assess heart rates using heart rate monitors (e.g., Polar or Zephyr Bioharness) and ratings of perceived exertion (RPE, Borg 6-20) throughout the supervised exercise sessions. We will also measure the subjects' weight once per week during one of their scheduled exercise visits.

	Mon	Tue	Wed	Thu	Fri
A. Resistance Exercise (RE)		
 • Leg Press • Leg Extension • Leg Curls • Chest Press • Lat Pulldowns • Shoulder Press • Triceps Extension • Biceps Curls 
3 Sets 10-12 Reps to Failure
		
 • Leg Press • Leg Extension • Leg Curls • Chest Press • Lat Pulldowns • Shoulder Press • Triceps Extension • Biceps Curls 
3 Sets 10-12 Reps to Failure
	
B. LPA Breaks in Sedentary Time*	6x10 min bouts at 2 METS	6x10 min bouts at 2 METS	6x10 min bouts at 2 METS	6x10 min bouts at 2 METS	6x10 min bouts at 2 METS
C. Aerobic Exercise	1 x50 min bouts at 4 METS		1 x50 min bouts at 4 METS		1 x50 min bouts at 4 METS

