Table 2. The RE group will complete supervised RE (2x/wk) (A). The REALPA breaks in ST group will complete supervised RE (2x/wk) and regular unsupervised LPA breaks in ST (5x/wk) (A+B). The RE+AE group will complete supervised RE (2x/wk) and calorically matched moderate intensity AE (3x/wk) (A+C).

Physical Activity Monitoring During Intervention. To quantify total physical activity throughout the intervention, we will ask that subjects wear a physical activity monitor (Actigraph, GT9X) on their wrist 24 h/d for the duration of the study and a second physical activity monitor (Actigraph, GT9X) on their thigh during weeks 1, 4, 8, 12, and 16 for further quantification. We will screen raw data from these monitors for periods of valid wear-time with a required minimum wear-time of 10 h per valid wear-day and 4 valid wear-days per week.^{23,24} We will use standard algorithms to characterize the patterns of PA and ST.²⁵

Adherence Monitoring During Intervention. We will monitor each subject's attendance to the prescribed exercise training sessions and exercise training logs to assess adherence to the exercise intervention. We will also use the physical activity monitoring data to help assess adherence to the exercise intervention. De-identified physical activity monitoring data will be uploaded to the CentrePoint Cloud-Based Data Capture and Management Platform to facilitate data collection and monitoring.

Visit 3 (V3) (End of Exercise Intervention). During last week of the intervention (i.e., week 16), subjects will be asked to complete V3, with two parts. Part I will occur PBRC and Part II at the LSU Exercise Physiology Laboratory on the main campus of LSU.

V3, Part I (about 2 hours).

After an overnight fast (> 10 hours), subjects will report to PBRC to complete V3, Part I. During this visit, we will measure height, weight and vital signs. We will then perform the SPPB and Exercise Test (VO₂ Peak).

V3, Part II (about 1 hour).

Subjects will report to LSU Exercise Physiology Laboratory to complete V3, Part II (non-fasted). The visit procedures for this visit can be done at a regularly scheduled exercise session and would be completed prior to the start of that day's exercise. During this visit, we will conduct the Biodex, 1-RM, and Handgrip Strength and Endurance Testing.

Posttraining Visit 4 (V4) (About 5 hours).

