Exercise Test – VO₂ Peak (about 1 hour). Prior to the first exercise test, subjects will complete a physical exam, medical history, resting EKG which will be reviewed by [name] (Medical Investigator) and/or other qualified practitioner. Exercise test will only proceed if subject qualifies. We will use an incremental treadmill protocol with indirect calorimetry (Parvo-Medics TrueOne) to measure VO₂ peak at PBRC in the Exercise Testing Core.¹⁶ Subjects will be asked to initially walk at 1.5 miles per hour at 0% grade for 5 minutes. Following this initial warm-up, subjects will begin walking at self-selected brisk walking speed at 0% grade. Thereafter the speed will remain constant and the grade will increase by 2% every 2 minutes until

volutional exhaustion. Once this is reached, a 5 minute cooldown starting at 1.5 mph and 0% grade will be initiated. During the cool-down, the speed will be gradually lowered by 0.5 mph each minute until 0 mph is reached. We will assess heart rate continuously using a 12 lead EKG, while blood pressure and ratings of perceived exertion (RPE, Borg 6-20) will be assessed every 2 minutes. According to PBRC SOP 1303 for exercise testing, a physician will be available in the building and may be present at the time of testing should any complications arise. During the test, subjects will be told that they can lightly grip the hand rails at any time if it makes them feel more secure while walking. Stopping rules for this test are consistent with other exercise testing procedures performed in the Exercise Testing Core as described in SOP 1303. The exercise EKG will be read by the study physician for any signs of abnormalities and will be documented and reported to the PI and the study medical investigator. The medical investigator will contact the subject to discuss any abnormal findings, and with the subjects permission may contact the subject's physician to facilitate appropriate follow-up.

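### Conditions before the primary isokinetic strength test are not matched between baseline and post-training, so within-group strength and muscle-quality gains can be inflated

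*Combined protocol and SAP*

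**What the plan says.** **Baseline.** The Screening Visits section says: "We will try and schedule Part I and II on the same day, but these visits may be conducted on separate days". Part I measures VO2 peak "using a cardiopulmonary exercise test". Under Detailed Methods (Exercise Test), "the grade will increase by 2% every 2 minutes until" the subject is exhausted. Part II is the baseline strength visit: "We will measure isokinetic strength and endurance of the knee extensors". No recovery time between the two parts is given. Part II also allows that "the 1-RM measurements may be performed prior to your regularly scheduled exercise session during the first and last week of the intervention", but this applies to the 1-RM tests and not to the Biodex test.

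**Post-training.** Both parts of V3 fall in week 16. Part I repeats the VO2 peak test. Part II repeats the Biodex, 1-RM and grip tests; it "can be done at a regularly scheduled exercise session and would be completed prior to the start of" that day's exercise. Nothing sets the order of the two parts, the gap between them, or the time since the last training session.

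**Other visits.** V4 is set at 48 hours after the last session and V5 at about 72 hours. Vigorous exercise is ruled out for 48 hours before V1 and V4.

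**Training days.** Table 2 puts resistance exercise on Tuesday and Thursday in all arms. RE+AE adds "1 x50 min bouts at 4 METS" on Monday, Wednesday and Friday, and REALPA adds light walking breaks from Monday to Friday. The Exercise Interventions section lets subjects vary their days.

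**Use.** Study Endpoints names within- and between-group change in strength and in muscle quality (strength/mass) as primary. Randomization follows baseline testing.

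**The concern.** A maximal voluntary test is sensitive to recent hard exercise. If the stated preference is followed, baseline knee-extensor torque is measured on the day of an exhaustive treadmill test. At V3 the test can be held fresh, ahead of a session. A low baseline against a rested follow-up looks like a training gain in every arm. Muscle quality, which has strength as its numerator, inherits the error.

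This matters because within-group change is itself a primary endpoint, and because the pilot exists to supply effect sizes for the follow-up application. An inflated change would carry into that planning. The plan already controls recent exercise before V4 and V5, but not before this primary measurement.

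**Working it through.** **1. The plan's own arithmetic.** 12 completers per group with 20% attrition: 12 / (1 − 0.20) = 15 per group, and 3 × 15 = 45. This reproduces. The documents give no SD, effect size or power for strength, so nothing more can be reproduced.

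**2. Conditions side by side.**

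| | Baseline (Screening Part II) | Post-training (V3 Part II) |
|---|---|---|
| VO2 peak test | same day preferred, and first (Part I) | same week, order and gap not stated |
| Gap since last training session | not applicable | not stated |
| Test before that day's exercise | no such rule | yes, if held at a session |

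**3. Rest at V3, counted from the Table 2 days** (hours since the last supervised session):

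| Test day | RE | REALPA | RE+AE |
|---|---|---|---|
| Mon | 96 | 96 | 72 |
| Tue | 120 | 120 | 24 (after AE; 120 since RE) |
| Wed | 24 | 24 | 24 (after RE) |
| Thu | 48 | 48 | 24 (after AE; 48 since RE) |
| Fri | 24 | 24 | 24 (after RE) |

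At their own sessions (Tuesday, Thursday), RE and REALPA subjects have 120 or 48 hours. RE+AE subjects have a session every weekday, so they have 24 hours on every day except Monday. REALPA also has 2-MET walking the day before on Tuesday to Friday. RE and REALPA share the same resistance schedule.

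**4. Effect of a baseline deficit on the apparent gain (assumed deficits).** With deficit f and true gain g, the apparent gain is (1 + g)/(1 − f) − 1.
- g = 0: f = 2%, 5%, 10% gives 2.0%, 5.3%, 11.1%.
- g = 10%: the same deficits give 12.2%, 15.8%, 22.2%.

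These assume that every subject is exposed; if only some have the same-day test, the mean deficit shrinks in proportion.

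**5. Effect on error rates (assumed artefact b, in SDs of change).** Two-sided 0.05, 12 per group, pooled error with 36 − 3 = 33 df, critical t = 2.03. Noncentrality is b√12 for one group's change, b√36 for the time effect over 36 completers, and b√(12/2) for a contrast of two arms in which only one carries the artefact.

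| b | Within group | Time effect | Arm-specific artefact, pairwise contrast |
|---|---|---|---|
| 0 | 5% | 5% | 5% |
| 0.1 | 6% | 9% | 6% |
| 0.25 | 13% | 31% | 9% |
| 0.5 | 39% | 83% | 22% |

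A single-group paired t test (11 df) gives 6%, 12% and 35% within group.

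**6. Which column applies.** Baseline fatigue occurs before randomization, so its expected value is the same in all arms and cancels from between-arm contrasts. It acts on the within-group and time-effect columns. Only unequal rest at V3 can act on the last column.

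**The case against.** The case against has real force.
- Same-day screening is a preference, and separate days are allowed. The two parts are at different sites, and strength testing starts with a treadmill warm-up and Biodex practice. No document says that fatigue persists to Part II.
- The follow-up is not guaranteed to be rested: V3 Part I is in the same week with no set order, so the post-training strength test could also follow a VO2 peak test.
- A within-group false-positive rate presumes no true gain, yet the protocol expects some improvement in all three arms. There is no non-exercising arm, so within-group change already contains learning and other time effects.
- Attendance, training logs and wrist monitoring would partly allow time since training to be reconstructed.

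All of this stands, and it limits the point to what can happen under the plan as written. It does not remove the mismatch: the stated preference at baseline favours the worse condition, and nothing at V3 offsets it by design.

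A reader might infer that RE+AE is materially disadvantaged against the other arms. The documents do not support that. The rest pattern is inferred from Table 2, whose days are flexible, and V3 Part II need not be held at a session. On Tuesday or Thursday the time since resistance exercise is the same in all arms, and the RE+AE difference is a 4-MET walk the day before. The less favourable case, a Wednesday or Friday test 24 hours after resistance work to failure, is permitted but not prescribed.

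**Conclusion.** The point holds as a possibility that the plan creates and could easily remove. Conditions before the primary strength test are uncontrolled at both time points, and the stated baseline preference is the unfavourable one. Within-group strength and muscle-quality gains and the time effect can be inflated. Between-arm contrasts are not biased in expectation by baseline fatigue. Unequal rest at V3 could slightly distort contrasts with RE+AE. The central RE versus REALPA contrast is probably little affected, since those arms differ only by 2-MET walking.

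A reader might infer that strength gains are biased, and by a known amount. The documents show neither; they give no fatigue size and no SD for torque. Assuming a torque CV of 25% and a pre-post correlation of 0.9, the SD of change is 25% × √(2 × 0.1) = 11.2%. A deficit of 3% to 8% in every subject then gives a within-group false-positive rate of 14% to 62% (11 df). With half the subjects exposed (mean shift 1.5% to 4%, ignoring added variance) it is 7% to 21%. With correlation 0.8 and full exposure it is 9% to 36%. That spread comes entirely from outside assumptions, so the rates for 0.1 to 0.5 SD are illustration, not an estimate.

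**What to change.** - In Screening Visits, replace the same-day preference with separate days, so that the Biodex test is never on the day of the VO2 peak test.
- Apply the same separate-day rule at V3 and state one test order for all arms: V3 Part II before V3 Part I, or otherwise on a later day.
- Hold V3 Part II before the first supervised session of the final week in every arm. On Table 2 days that is Monday for RE+AE (72 hours since Friday) and Tuesday for RE and REALPA (120 hours since Thursday). Every arm then has at least 72 hours since supervised training, with no session moved or dropped.
- Record hours since the last session (post-training) and since the VO2 peak test (both time points).

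A bare 48-hour minimum would do less. On Table 2 days RE+AE meets it only on Monday, and 48 hours in one arm with 120 in another would comply.

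The cost is one extra trip for subjects who would have combined the screening parts, and slightly less scheduling flexibility in week 16. Separate screening days are already permitted.

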Phosphorous Magnetic Resonance Spectroscopy – ^{31}P -MRS (about 45 minutes). We will use phosphorus magnetic resonance spectroscopy (^{31}P -MRS), to measure *in vivo* mitochondrial oxidative capacity.³⁰ These measurements will be performed in the PBRC Imaging Core. This test involves measurement of skeletal muscle phosphocreatine during resting conditions and after performing leg contractions in the MRI scanner. The aim of this test is to calculate the rate of phosphocreatine recovery after dynamic leg extension inside of a MRI, which is used as an *in vivo* marker of oxidative capacity in the skeletal muscle. Prior to testing, study subjects must be rested for a minimum of 3 hours after their last exercise regimen. This scan will take approximately 45 minutes in total to complete. Subjects will be positioned supine on the 3.0 T magnet with only the lower extremity inside the bore. The ^{31}P RF coil will be positioned over the right *vastus lateralis* (or left if the person has a medical reason not to use the right leg). The ankles and femur will be secured to each other with Velcro or nylon sports straps to create some resistance for the dynamic kicking exercise required for the test. A scout scan is performed first in order to visually locate the *vastus lateralis* muscle. Next, ^{31}P spectra is acquired every 60 seconds for 2 minutes to achieve baseline [PCr], [ATP] and [Pi] while the subject rests in the scanner. The subject will then be prepared for the dynamic leg extension exercise. The dynamic 1D- ^{31}P MRS scan will be set up as follows: Time to repetition 1.5 s, acquire average spectra at a rate of 6 seconds per spectrum for a total of 75 spectra (estimated prescription time, 7 minutes 30 seconds). This pulse sequence will run for 36 seconds (i.e. 6 spectra) before instructing the subject to perform the leg extension exercise. When instructed, the subject will be asked to kick the right leg (or the leg surrounded by the coil) hard and fast for approximately 28 seconds against the Velcro or nylon strap. The ^{31}PCr peak will be monitored in real-time. We will determine if the reduction in PCr is 35 to 45 percent of baseline ^{31}PCr and will instruct the subject to stop at this moment. Alternatively, if this 35-40% reduction is not met, we may start the dynamic scan until the first four spectra are acquired then pause the scan and calculate 40% of the baseline PCr peak. This value can then be used for the target signal in the real-time display mode and we will start the scan with the exercise and instruct the subject to stop at the moment the target signal is observed. In the event that we overshoot the target signal, we will allow the subject to rest and relax for 10 minutes then repeat the leg extension exercise. This scan is for research purposes only and not for diagnostic treatment.

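### Read literally, the optional 31P-MRS fallback targets a 60% fall in PCr, while the main procedure stops at 35-45%; the sentences need reconciling (low severity)

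*Combined protocol and SAP*

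**What the plan says.** The subsection on phosphorus spectroscopy, under Detailed Methods and Analysis, describes two ways to decide when the subject stops kicking in the scanner.

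- **Main route.** The PCr "peak will be monitored in real-time". The stopping criterion is a fall from baseline: "We will determine if the reduction in PCr is 35 to 45 percent of baseline", and the subject is told to stop at that point.
- **Fallback route.** This begins "Alternatively, if this 35-40% reduction is not met", so the upper limit of the window is now 40% and not 45%. Staff may then start the dynamic scan, collect four spectra, and "pause the scan and calculate 40% of the baseline PCr peak". The text continues: "This value can then be used for the target signal in the real-time display mode". Staff then "instruct the subject to stop at the moment the target signal is observed".
- **Overshoot rule.** "In the event that we overshoot the target signal, we will allow the subject to rest and relax for 10 minutes", after which the exercise is repeated.

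The scan is scheduled at V2 and V5 (Table 1 and the visit descriptions). No other section restates or corrects these percentages.

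**The concern.** The two routes use a percentage in different senses. The main route uses the amount lost from baseline. The fallback takes a fraction of the baseline peak and makes that fraction the signal level to be reached. Because the displayed peak falls during exercise, a target level of 40% of baseline is reached only after 60% has been lost.

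At stake is whether scans in the same study are stopped at comparable depletion. The section specifies a window and a repeat after overshoot, so depletion is evidently meant to be controlled. An operator who enters the calculated number as written would apply a deeper stopping point to fallback scans than to the rest. PCr recovery could then be less comparable between subjects, or between one subject's V2 and V5 scans if the routes differ.

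The two statements of the window add a smaller uncertainty about when the fallback applies. A 43% reduction satisfies the 35-45% window but not the 35-40% one.

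**Working it through.** **Inputs**, all from the 31P-MRS subsection:

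- Main-route reduction: 35-45% of baseline.
- Window as restated at the start of the fallback: 35-40%.
- Fallback value: 0.40 × baseline PCr peak, used as the target signal.

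**Formula.** Reduction = 1 − (signal at stop ÷ baseline signal). Set baseline = 100.

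**Step 1: signal left under the main route.**

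- 35% reduction: 100 − 35 = 65
- 40% reduction: 100 − 40 = 60
- 45% reduction: 100 − 45 = 55

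The main route therefore stops with 55-65% of the baseline signal remaining. The restated 35-40% window leaves 60-65%.

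**Step 2: reduction implied by the fallback target.** The target signal is 0.40 × 100 = 40, so the reduction is 1 − 40/100 = 60%. This lies outside both windows.

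**Step 3: size of the gap.**

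- 60 − 45 = 15 and 60 − 35 = 25, so the fallback is 15-25 percentage points deeper than the main route.
- As ratios: 60/45 = 1.33, 60/40 = 1.50 and 60/35 = 1.71.

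**Step 4: other readings.**

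| Reading | Signal at stop | Reduction | Agrees with the text? |
|---|---|---|---|
| 40% is the target signal (literal) | 40 | 60% | No: outside both windows |
| 40% is the size of the drop | 60 | 40% | Inside both windows, but the text makes the calculated value the target itself and never says to subtract it |
| 35-45% is the signal remaining | 35-45 | 55-65% | A target of 40 would fit, but both sentences call the figure a reduction |

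No reading makes all the sentences agree.

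**Step 5: does the overshoot rule catch it?** Take a subject at 50% depletion on the fallback route. The signal is 50. That is past the main route's 45% limit, but it is still above the fallback target of 40. Under the literal rule there is no overshoot, and the subject continues.

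**The case against.** The strongest reply is that this is loose wording and not a real 60% target. The fallback sentence is about missing a reduction window, and 40% sits inside both versions of that window. It would also be odd to set a 60% depletion for someone who has just failed to reach 35%. This has force: a 40% drop was probably intended, and trained staff may well apply it that way. It does not remove the fault, because the instruction as written names the calculated value as the target and nothing tells the operator to subtract it.

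Three further points limit the consequence, and all stand.

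- **The fallback is optional.** The text says staff may use it, and gives no indication of how many scans would need it.
- **The measure is a supporting one.** Under Specific Aim 1 the secondary muscle outcomes are oxidative phosphorylation capacity by high-resolution respirometry and oxidative protein damage by immunoblotting. The Study Endpoints section does not list 31P-MRS, and the planned ANOVA models are for the primary outcomes.
- **All three arms follow the same scan procedure.** The documents give no reason to expect fallback use to differ between arms.

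A reader might go further and infer that trained legs reach the target more easily, so that fallback use would shift between V2 and V5 and confound the change in oxidative capacity. The documents do not support this. They do not say whether training makes the target easier or harder to reach. Nor do they say how the recovery measure depends on depletion: the plan speaks of a recovery rate without stating whether this is an initial rate or a rate constant.

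**Conclusion.** The fallback instruction is wrong as written, at low severity. Taken literally, it sets a 60% reduction against the main procedure's 35-45%, a gap of 15-25 percentage points, and the overshoot rule does not correct it. The window itself is also stated in two ways.

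This conclusion rests only on the wording of the one subsection and on subtraction. It assumes that the on-screen target is the height of the PCr peak, as the text indicates. The consequence is conditional: if the fallback is used, and is applied literally, those scans stop at a different depletion from the others, which could reduce comparability between subjects or visits. The documents allow no estimate of how often this would happen, or of the size or direction of any effect on PCr recovery. They do not support concluding that scans will in fact be run to 60% depletion, or that a trial endpoint is biased.

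**What to change.** Reconcile the sentences in the 31P-MRS subsection.

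1. Give one reduction window and use it in both the main and the fallback sentences. Which window applies is for the investigators to decide.
2. State for each percentage whether it is the drop from baseline or the signal remaining.
3. Make the fallback target consistent with that choice. If the plan's 40% reduction is kept, the target signal is 100% − 40% = 60% of the baseline PCr peak. The overshoot rule then refers to the same depletion on both routes.

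Optionally, record for each scan which route was used and what depletion was achieved, so that comparability can be checked at analysis.

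The cost is a small edit to one procedure description. The optional record adds two data fields per scan. No extra scans or visits are needed.
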